11.2. Modification of Dose and/or Treatment Schedule

11.2.1. Dosing Interruption for Abnormal Laboratory Values

Study treatment must be temporarily withheld when any of the following laboratory values meet the threshold limits defined in [Table 3](#); laboratory abnormalities that require immediate and permanent discontinuation of study treatment are also specified.

Table 3: Laboratory Criteria Requiring Withholding or Permanent Discontinuation of Treatment

Laboratory Parameter	Laboratory Result	Required Action
AST (SGOT) or ALT (SGPT)	$>3 \times \text{ULN}$	The Investigator should repeat the test as soon as possible. If the retest value confirms AST or ALT $>3 \times \text{ULN}$, the study treatment must be withheld. If the value remains $>3 \times \text{ULN}$ for ≥ 4 weeks after discontinuation of study treatment, then the subject must permanently discontinue study treatment, and the event must be recorded as an AE .
Creatinine	$>1.2 \times \text{ULN}$	The Investigator should repeat the test as soon as possible. If the retest value confirms that creatinine is $>1.2 \times \text{ULN}$, the study treatment must be withheld. If the value remains $>1.2 \times \text{ULN}$ for ≥ 4 weeks after discontinuation of study treatment, then the subject must permanently discontinue study treatment, and the event must be recorded as an AE .

CONFIDENTIAL

The information contained herein may not be used, disclosed, or published without the written consent of
Biogen MA Inc.

Laboratory Parameter	Laboratory Result	Required Action
WBC	<2000/mm ³	The Investigator should repeat the test as soon as possible. If retest value confirms that WBC count is <2000/mm ³ , the study treatment must be withheld. If the value remains <2000/mm ³ for ≥4 weeks after discontinuation of study treatment, then the subject must permanently discontinue study treatment, and the event must be recorded as an AE.

AE = adverse event; ALT = alanine transaminase; AST = aspartate transaminase; SGOT = serum glutamic oxaloacetic transaminase; SGPT = serum glutamic pyruvic transaminase; ULN = upper limit of normal; WBC = white blood cell.

While dosing is withheld, subjects will continue tests and assessments according to the schedule defined in Section 4.2 (and may also undergo additional assessments to evaluate the laboratory abnormality as per the Investigator's standard practice). In addition, subjects (whether dosing is temporarily withheld or permanently discontinued) must have the abnormal laboratory result retested at least every 2 weeks (retests will be run at the central laboratory) until resolution or stabilization of the laboratory value. Depending on the severity and clinical significance of the abnormality, the Investigator may need to perform the retests more frequently.

11.2.2. Resumption of Study Treatment Dosing

Resumption of study treatment is to be considered on a case-by-case basis and must be discussed with the Medical Monitor. However, subjects who have abnormal laboratory values, as described in Table 3, sustained on 3 consecutive occasions (i.e., for more than 4 consecutive weeks) must permanently discontinue study treatment (Section 10.1). Subjects who have temporarily withheld BG00012 due to lymphopenia may resume BG00012 according to Section 11.3.

Subjects with abnormal laboratory values after Week 12 (after which clinic visits occur once every 3 months), who are allowed to resume study treatment dosing following a 2- to 4-week interruption, will restart dosing at a reduced dose for 1 week. Subjects must also return to the initial every-4-week visit schedule for safety assessments (see Table 1) for 2 consecutive normal laboratory assessments before reverting to the every-3-month schedule. Subjects will take 120 mg BID for 1 week. After 1 week at the reduced dose, subjects will take 240 mg BID.

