10. DISCONTINUATION OF STUDY TREATMENT AND/OR WITHDRAWAL OF SUBJECTS FROM THE STUDY

10.1. Discontinuation of Study Treatment

A subject *must* permanently discontinue study treatment for any of the following reasons:

- The subject becomes pregnant. Study treatment must be discontinued immediately. Report the pregnancy according to the instructions in Section 15.4.1.
- The subject withdraws consent to continue study treatment.
- The subject experiences a medical emergency that necessitates permanent discontinuation of study treatment.
- The subject is unable to tolerate study treatment at 240 mg BID (see Section 11.2.4).
- The subject receives any concomitant medications not allowed by the protocol.
- The subject experiences any of the laboratory abnormalities requiring permanent discontinuation of treatment defined in [Table 3](#).
- The subject experiences more than 1 deviation of the same laboratory parameter that meets the threshold limits defined in [Table 3](#) at any time during the study.
- The subject experiences more than 2 different deviations of laboratory parameters that meet the threshold limits defined in [Table 3](#) at any time during the study. On a third occasion, the subject is required to discontinue dosing for the remainder of the study.
- If a subject has a lymphocyte count $<500/\text{mm}^3$ persisting for more than 24 weeks consecutively, study treatment must be temporarily withheld. Study treatment may be resumed after lymphocyte counts recover $>\text{LLN}$ on 2 consecutive occasions at least 4 weeks apart. If the subject develops a lymphocyte count $<500/\text{mm}^3$ on 1 occasion (confirmed by repeat testing) on resumption of study treatment, the subject must permanently discontinue study treatment and will continue protocol-required visits and assessments (see Section 11.3).
- If a subject's lymphocyte count remains $<\text{LLN}$ for 24 weeks consecutively after study treatment has been temporarily withheld due to lymphocyte count $<500/\text{mm}^3$ for more than 24 weeks, the subject must permanently discontinue study treatment.
- At the discretion of the Investigator for medical reasons or for noncompliance.

The reason for discontinuation of study treatment must be recorded in the subject's case report form (CRF).

Subjects who discontinue treatment may remain in the study and continue protocol-required tests and assessments.

CONFIDENTIAL

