11.2.3. Subsequent Development of Additional Laboratory Abnormalities

Subjects who develop a subsequent abnormal value for the same laboratory parameter at any other time during the study must permanently discontinue dosing with study treatment, i.e., only 1 dosing interruption is allowed for each subject for the same laboratory abnormality. However, subjects who subsequently experience an abnormality of a different laboratory parameter can have study treatment withheld again. For example, if a subject had dosing temporarily withheld for an abnormal ALT/SGPT, then had dosing resumed after ALT/SGPT returned to acceptable limits, and subsequently developed abnormal white blood cells (WBCs), the subject may have

CONFIDENTIAL

The information contained herein may not be used, disclosed, or published without the written consent of Biogen MA Inc.

study treatment withheld again. However, only 2 dosing interruptions are allowed for each subject.

Any subject who experiences abnormal laboratory results that meet the criteria defined in [Table 3](#) on a third occasion must permanently discontinue dosing.

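### Section 11.2.2 equates three consecutive abnormal results with more than 4 weeks; the 2-weekly retest schedule does not give this, and Table 3 sets a different permanent-stop threshold

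*Protocol*

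**What the plan says.** All references are to protocol Version 2 and to the laboratory parameters in Table 3 (ALT/AST, creatinine, WBC). Lymphocyte counts have their own rules in Section 11.3.

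- **Section 11.2.1, Table 3.** After an abnormal value, "The Investigator should repeat the test as soon as possible". If the retest confirms it, drug is withheld. The stop becomes permanent if the value stays beyond the limit for "≥ 4 weeks after discontinuation of study treatment, then the subject must permanently discontinue study treatment". The protocol Table 2 footnotes and the SAP copy of that table repeat this rule.
- **Section 11.2.1, text after Table 3.** Subjects off drug "must have the abnormal laboratory result retested at least every 2 weeks", and depending on severity "the Investigator may need to perform the retests more frequently".
- **Section 11.2.2.** Restart is decided case by case with the Medical Monitor. As an exception, subjects with Table 3 values "sustained on 3 consecutive occasions (i.e., for more than 4 consecutive weeks) must permanently discontinue study treatment". The section cites Section 10.1 for this and does not say when the count starts. It also describes restart after an interruption of 2 to 4 weeks.
- **Section 10.1.** Permanent stop if "The subject experiences more than 1 deviation of the same laboratory parameter that meets the threshold limits" in Table 3. It contains no three-occasion rule; its only bullet on a single persisting abnormality points back to Table 3.
- **Section 11.2.3.** On recurrence, "only 1 dosing interruption is allowed for each subject for the same laboratory abnormality". It also allows two interruptions per subject in all.

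**The concern.** Section 11.2.2 presents a count of results and a length of time as the same thing. If they differ on the protocol's own retest schedule, a site following the count and a site following the time will reach different decisions on the same results. Table 3 adds a second duration rule with a different inequality (at least, rather than more than, 4 weeks) and with a start point that Section 11.2.2 lacks.

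At stake is a mandatory permanent stop. For some patients the wording decides whether treatment ends or restart may be discussed. It also affects reporting: SAP Section 5.4.1 tabulates adverse events leading to discontinuation separately from those leading to temporary interruption.

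**Working it through.** **Inputs**
- First abnormal value: Day 1.
- Confirming test and start of withholding: Day *c*. The protocol gives no number of days. *c* = 5 is an illustration and 2 to 16 is the range tried. Withholding is assumed to start on the day of the confirming test.
- Retest spacing: *s* ≤ 14 days (Section 11.2.1).
- Section 11.2.2: 3 occasions, said to equal more than 28 days.
- Table 3: at least 28 days from stopping drug.

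**Step 1: try to reproduce the stated equivalence**

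Counted from the confirming test, three occasions span 2*s*. At the longest spacing this is 2 × 14 = 28 days: exactly 4 weeks, not more. With weekly retests it is 2 × 7 = 14 days.

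Counted from the first value, they span (*c* − 1) + *s*. With *s* = 14 this is *c* + 13:
- *c* = 2: 15 days
- *c* = 5: 18 days
- *c* = 8: 21 days
- *c* = 15: 28 days
- *c* = 16: 29 days

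The span exceeds 28 days only if confirmation comes on Day 16 or later, which hardly fits a test to be repeated as soon as possible. The equivalence is not reproduced from either start.

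For *c* = 5, counting from the first value, exceeding 28 days takes four occasions at 14-day spacing (Days 1, 5, 19, 33) and six at 7-day spacing (Days 1, 5, 12, 19, 26, 33).

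**Step 2: set the rules on one timeline**

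| Rule, for a value that stays abnormal | Formula | *c* = 2 | *c* = 5 | *c* = 8 |
|---|---|---|---|---|
| Third occasion from first value, 14-day retests | *c* + 14 | Day 16 | Day 19 | Day 22 |
| Third occasion from confirming test, 7-day retests | *c* + 14 | Day 16 | Day 19 | Day 22 |
| Third occasion from confirming test, 14-day retests | *c* + 28 | Day 30 | Day 33 | Day 36 |
| Table 3, at least 4 weeks off drug | *c* + 28 | Day 30 | Day 33 | Day 36 |
| More than 4 weeks off drug, first seen on a 14-day grid | *c* + 42 | Day 44 | Day 47 | Day 50 |

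**Step 3: one patient, two instructions**

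Take *c* = 5, with abnormal values on Days 1, 5 and 19 and a normal value before Day 33, say Day 26.
- Occasion count including the first value: permanent stop on Day 19, which is 19 − 5 = 14 days off drug.
- Table 3: the value was not abnormal for 28 days off drug, so no permanent stop. On Day 26 the interruption is 26 − 5 = 21 days, inside the 2- to 4-week range for which Section 11.2.2 describes restart.

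With weekly retests the same split arises without counting the first value: Days 5, 12 and 19 are three occasions in 14 days.

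**Step 4: the counting units**

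*Occasion* is a test result in Section 11.2.2 but a separate event in the third-occasion sentences of Sections 10.1 and 11.2.3. Section 10.1 counts *deviations*, undefined. Section 11.2.3 speaks first of a later abnormal value, then of dosing interruptions. For lymphocytes, Section 10.1 requires a recurrent low value to be confirmed by repeat testing; the Table 3 recurrence bullets say nothing on this. The sentence allowing two interruptions is not expressly limited to Table 3.

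**The case against.** The best defence is that Section 11.2.2 refers to values as described in Table 3, where action follows confirmation, so the count should start at the confirming test. On 2-weekly retests the third occasion is then Day 33, exactly when Table 3 is met. What remains is at least versus more than 4 weeks, and measured from withholding the stricter Table 3 threshold is always reached first. Drug is withheld from confirmation throughout, and any restart goes through the Medical Monitor.

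Part of this stands. No tenable reading keeps the patient on drug between confirmation and normalisation, and the Day 19 stop with 2-weekly retests requires counting the first value and setting aside the parenthesis in the same sentence. But the agreement depends on a start point that the section does not state and on retests exactly 14 days apart, although shorter spacing is expressly allowed. Medical Monitor review does not settle it either, because the mandatory-stop sentence is written as an exception to that discretion.

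Two stronger readings are tempting and are not supported:
- A reader might infer that Section 10.1 forces a permanent stop at the confirming retest, as a second deviation. That would leave Table 3's temporary withholding and 4-week clause without use, and Section 11.2.3 explains the recurrence rule by dosing interruptions. It is an undefined term, not a third competing rule.
- A reader might infer that a lymphopenia interruption uses up one of the two allowed. The Table 3 context in Sections 10.1 and 11.2.3, and the separate lymphocyte rules in Section 11.3, largely answer this; the sentence only needs its scope stated.

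**Conclusion.** The point holds in a limited form. Three consecutive occasions are not more than 4 weeks on the protocol's schedule: at most 28 days from the confirming test, and 15 to 21 days from the first value if confirmation falls on Days 2 to 8 and retests are 14 days apart. Table 3 sets a different inequality and is the only one of the two rules with a start point. Some patients can therefore be a mandatory permanent stop under one sentence and a restart candidate under another. The inconsistent terms in Sections 10.1, 11.2.2 and 11.2.3 are a lesser ambiguity.

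The calendar days are illustrative: they rest on the assumed confirmation day, on withholding that same day, and on the retest spacing. The documents give no frequency of confirmed Table 3 values, so the number affected is unknown. A reader might infer an effect on the Week 48 lymphocyte-subset results. The documents do not show one: subjects who discontinue treatment may stay in the study with assessments continuing, and the pharmacodynamic population does not exclude them.

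**What to change.** Reconcile Sections 10.1, 11.2.1 (Table 3), 11.2.2 and 11.2.3:

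- State one start point for the persistence clock: first abnormal value, confirming test or start of withholding.
- State one threshold, either at least or more than 4 weeks.
- Remove the equivalence between three occasions and a number of weeks, or correct it so that it is true on the retest schedule.
- Define one counting unit for recurrence, say whether the confirming retest belongs to the same episode and whether a recurrence must itself be confirmed, and use *occasion* in one sense only.
- State whether the limit of two interruptions covers Table 3 only.

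The Table 2 footnotes in the protocol and the SAP already match Table 3 and need editing only if Table 3 changes. Which rule to adopt is the sponsor's medical decision. The cost is wording in an amendment or clarification letter, with no new visits, tests or patients.

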11.2.3. Subsequent Development of Additional Laboratory Abnormalities

Subjects who develop a subsequent abnormal value for the same laboratory parameter at any other time during the study must permanently discontinue dosing with study treatment, i.e., only 1 dosing interruption is allowed for each subject for the same laboratory abnormality. However, subjects who subsequently experience an abnormality of a different laboratory parameter can have study treatment withheld again. For example, if a subject had dosing temporarily withheld for an abnormal ALT/SGPT, then had dosing resumed after ALT/SGPT returned to acceptable limits, and subsequently developed abnormal white blood cells (WBCs), the subject may have

CONFIDENTIAL

The information contained herein may not be used, disclosed, or published without the written consent of Biogen MA Inc.

study treatment withheld again. However, only 2 dosing interruptions are allowed for each subject.

Any subject who experiences abnormal laboratory results that meet the criteria defined in [Table 3](#) on a third occasion must permanently discontinue dosing.

11.2.4. Dosage Reductions

Dosage reduction will be allowed only for subjects who are unable to tolerate study treatment due to flushing and/or GI disturbances (dosage reductions will not be allowed for abnormal laboratory values; for management of abnormal laboratory values, refer to Sections [11.2.1](#), [11.2.2](#), and [11.2.3](#)). Subjects who do not tolerate study treatment will reduce their dosage by taking 120 mg BID for up to 4 weeks. Within 4 weeks at the reduced dosage, subjects will resume taking the full dose of 240 mg BID. If the subject is still unable to tolerate study treatment, the subject must discontinue study treatment as described in Section [10.1](#). Subjects who do not tolerate study treatment will complete the final Follow-Up Visit 4 weeks after their last dose of study treatment and will then be withdrawn from the study (Section [10](#)).

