¹ Subjects will have a final Follow-Up Visit 4 weeks after taking their final dose, regardless of whether they complete the treatment period or discontinue prematurely, unless they have a lymphocyte count <LLN. Subjects who have a lymphocyte count <LLN will continue protocol-required visits and assessments per Section 11.3.

² Written informed consent must be obtained prior to performing any study-related procedures.

³ Medical history will include gastrointestinal abnormalities within the previous 6 months, as well as duration of MS (time since diagnosis), relapse history, and treatments for MS.

⁴ HIV testing will be done locally at Screening only if required, per local guidelines.

⁵ If required per local guidelines and if not already available within the previous 3 months, an MRI scan should be performed locally before starting therapy with BG00012.

⁶ Physical examination includes height and weight measurements, as well as a neurological examination.

⁷ Vital signs will include diastolic and systolic blood pressure, heart rate, and temperature. Subjects must be seated for 5 minutes prior to having their pulse and blood pressure measured.

⁸ Whole blood may also be collected for lymphocyte functional tests. Lymphocyte subset analysis will include total Ig and IgG subclasses, and may also include assays for [REDACTED] and VLA-4 expression. In subjects with a confirmed lymphocyte count <500/mm³ lymphocyte testing must be performed every 4 weeks; if the lymphocyte count remains <500/mm³ for 24 weeks, study treatment will be temporarily withheld for 24 weeks or until the lymphocyte count recovers to LLN, whichever is sooner, and testing continues to be every 4 weeks; if the lymphocyte count does not recover to LLN within 24 weeks while study treatment is temporarily withheld, study treatment will be withheld permanently, and testing will be performed every 12 weeks for an additional 24 weeks or until the lymphocyte count recovers to LLN, or until the end of the study, whichever is sooner.

⁹ Females of childbearing potential only. Results must be known to be negative prior to dispensing BG00012.

¹⁰ Pregnancy test may be repeated locally at additional timepoints if needed, per local guidelines.

¹¹ Sample can be collected at any point during the study in subjects who have signed a separate informed consent form.

CONFIDENTIAL

The information contained herein may not be used, disclosed, or published without the written consent of Biogen MA Inc.

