7.2.3. Follow-Up

[figure not shown]
Subjects are to return to the study site for a Follow-Up Visit 4 weeks after their last dose of study treatment. The final study visit will be Week 100.

Subjects who temporarily withhold or permanently discontinue BG00012 for any reason and have a lymphocyte count <LLN will be followed every 4 weeks for 24 weeks, then every 12 weeks (**unless clinically indicated more often or at the Investigator's discretion**) until the lymphocyte count is \geq LLN or for up to 48 weeks following drug discontinuation, whichever occurs sooner; see [Section 11.3](#)). Subjects whose lymphocyte count remains <LLN at the end of the study (Week 96) will complete the final Follow-Up Visit and will then be followed up outside of this protocol at the Investigator's discretion.

CONFIDENTIAL

The information contained herein may not be used, disclosed, or published without the written consent of
Biogen MA Inc.

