10.2. Withdrawal of Subjects From Study

Subjects must be withdrawn from the study for any one of the following reasons:

- The subject is unable to tolerate study treatment at 240 mg BID (see Section 11.2.4).
- The subject withdraws consent.
- The subject enrolls into another interventional clinical study in which an investigational treatment or approved therapy for investigational use is administered.
- The subject is unwilling or unable to comply with the protocol.

For details regarding follow-up for subjects who discontinue study treatment or withdraw from the study, see Section 7.2.3.

The reason for the subject's withdrawal from the study must be recorded in the subject's CRF.

Subjects who withdraw from the study for reasons other than safety may be replaced at the discretion of Biogen.

CONFIDENTIAL

The information contained herein may not be used, disclosed, or published without the written consent of
Biogen MA Inc.

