11.3.2. Schedule for Subjects With Lymphocyte Counts <LLN to $\geq 500/\text{mm}^3$

Subjects with lymphocyte count <LLN to $\geq 500/\text{mm}^3$ will have tests and assessments according to the schedule defined in Section 4. If these subjects complete, temporarily withhold, or permanently discontinue study treatment for any reason, they will be followed as described in Section 11.3.3.

11.3.3. Schedule for Subjects Who Temporarily Withhold or Permanently Discontinue Study Treatment for Any Other Reason Than Lymphopenia and Have a Lymphocyte Count <LLN

[figure not shown]
Subjects who temporarily withhold or permanently discontinue BG00012 for any other reason than lymphopenia (see Section 11.2) and who have a lymphocyte count <LLN will be followed every 4 weeks for 24 weeks, then every 12 weeks (**unless clinically indicated more often or at the Investigator's discretion**) until the lymphocyte count is $\geq \text{LLN}$ or for up to 48 weeks following drug discontinuation, whichever occurs sooner. Subjects who temporarily withhold or permanently discontinue study treatment and have a lymphocyte count <LLN for 48 weeks should continue tests and assessments according to the schedule defined in Section 4 until the lymphocyte count recovers or until the final Follow-Up Visit (whichever is sooner). Subjects whose lymphocyte counts remain <LLN at the end of the study (Week 96) will complete the final Follow-Up Visit and will then be followed up outside of this study at the Investigator's discretion.

See [Figure 3](#) for a schedule of subjects who complete, temporarily withhold, or permanently discontinue BG00012 for any other reason and who have a lymphocyte count <LLN.

CONFIDENTIAL

The information contained herein may not be used, disclosed, or published without the written consent of
Biogen MA Inc.

Figure 3: Schedule for Subjects Who Temporarily Withhold or Permanently Discontinue Study Treatment for Any Other Reason Than Lymphopenia* and Have Lymphocyte Count <LLN

LLN = lower limit of normal.

*For subjects with low lymphocytes, refer to Section 11.3.1 and 11.3.2.

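### Protocol 11.2.4 withdraws drug-intolerant subjects after a 4-week visit with no exception for a low lymphocyte count, against the follow-up of up to 48 weeks required elsewhere (minor)

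*Protocol*

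**What the plan says.** Section numbers refer to protocol Version 2.

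**The withdrawal rule.** Under 11.2.4, a subject who still cannot tolerate the drug after a temporary dose reduction completes the final Follow-Up Visit "4 weeks after their last dose of study treatment and will then be withdrawn from the study". Section 10.2 opens with "Subjects must be withdrawn from the study for any one of the following reasons" and lists "The subject is unable to tolerate study treatment at 240 mg BID" among the reasons. It gives no timing. Neither place mentions the lymphocyte count. Section 10.2 does add: "For details regarding follow-up for subjects who discontinue study treatment or withdraw from the study, see Section 7.2.3".

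**The lymphocyte follow-up rule.** Under 7.2.3, those who "permanently discontinue BG00012 for any reason and have a lymphocyte count <LLN will be followed every 4 weeks for 24 weeks". The interval afterwards is 12 weeks, and follow-up ends on recovery to at least LLN or at 48 weeks from discontinuation at the latest. A temporary interruption is treated the same way. Section 11.3.3 sets the same schedule for those who "permanently discontinue BG00012 for any other reason than lymphopenia (see Section 11.2) and who have a lymphocyte count <LLN". Table 1 footnote 1 applies the 4-week final visit to all subjects "regardless of whether they complete the treatment period or discontinue prematurely, unless they have a lymphocyte count <LLN", and sends those with a low count to Section 11.3. Table 2 footnote 3 and SAP 5.3.3 also apply the follow-up whatever the reason for stopping.

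**The concern.** A subject who stops for intolerance while ALC is below LLN (0.91 x 10^9/L in SAP 5.3.1) falls under both rules. One ends participation after a visit at week 4. The other keeps the subject on study for up to 48 weeks. A site cannot do both. Table 2 footnote 2 defines withdrawal as leaving the study, so the word cannot be read as merely stopping drug.

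Section 11.2.4 is where a site looks when a subject does not tolerate the drug, and its sequence is explicit. Followed literally, it ends protocol monitoring before it is known whether the count recovers. Protocol 5.3.2 reports progressive multifocal leukoencephalopathy (PML) with prolonged moderate to severe lymphopenia, so seeing recovery is the purpose of the follow-up. The recovery summary in SAP 5.3.3 would also lose these subjects after its first window, and the SAP imputes no missing data.

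**Working it through.** No figure in the plan is in dispute. The check compares the two rules, then sizes the loss.

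**1. Which rule governs a subject stopping for intolerance with ALC <LLN?**
- 11.2.4 and 10.2: withdraw; 11.2.4 places this after the 4-week visit. No lymphocyte condition.
- 7.2.3: follow, whatever the reason for stopping.
- 11.3.3: follow, for any reason other than lymphopenia. It cites Section 11.2, the parent of 11.2.4, so intolerance is covered.
- Table 1 footnote 1: the 4-week final visit does not apply when ALC is <LLN.
- 10.2 cross-reference: withdrawn subjects are sent to 7.2.3.

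The last four point the same way, but nothing in 11.2.4 says so. Figure 3, the schedule for stops other than for lymphopenia, is not shown in the text available, so whether it settles the order is unknown.

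**2. Loss per affected subject who does not recover.**
- Scheduled lymphocyte visits after stopping: weeks 4, 8, 12, 16, 20, 24, 36 and 48, which is 8. SAP Appendix 2 has the 8 matching windows.
- Counting the stop date as Day 1, the Discontinuation Visit (within 2 weeks) falls by Day 15. The final visit (28 +/-5 days after the last dose) falls on Day 24 to 34.
- Both lie in the first window, Day 2 to 42. Windows left empty: 8 - 1 = up to 7. Follow-up lost: 48 - 4 = up to 44 weeks.
- A subject who recovers by week 4 loses nothing.

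**3. How many subjects?** The documents give no rate of stopping for intolerance, so this is an illustration.

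Early-stop assumptions:
- Stops for intolerance in 2% to 10% of 200: 200 x 0.02 = 4 to 200 x 0.10 = 20. The top end uses the whole planned discontinuation allowance.
- Stops at Weeks 4 to 12, because 5.3.2 says flushing and gastrointestinal events tended to decline after the first month.
- Low ALC accrues linearly to the 48-week rates in Protocol 16.7 (16% with at least 2 low values, 24% with at least 1): 16% x 4/48 = 1.3% to 24% x 12/48 = 6.0%.
- Expected number: 4 x 0.0133 = 0.05 to 20 x 0.06 = 1.2.

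Sensitivity, applying the full 48-week rates whatever the time of stopping, with 25% to 100% of discontinuations due to intolerance:
- At 10% discontinuation: 200 x 0.10 x 0.25 x 0.16 = 0.8 to 200 x 0.10 x 1.00 x 0.24 = 4.8.
- At 5% to 20% discontinuation: 200 x 0.05 x 0.25 x 0.16 = 0.4 to 200 x 0.20 x 1.00 x 0.24 = 9.6.

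The second set is a ceiling for early stops, since it credits a subject stopping in the first months with a full year's risk. Both sets count any low value rather than a low value at stopping, so they tend to overcount.

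**The case against.** The best defence is that the protocol already resolves the order. The visit named in 11.2.4 is the Table 1 final Follow-Up Visit. That visit's own footnote exempts subjects with ALC <LLN, and 10.2 sends withdrawn subjects to 7.2.3. The lymphocyte rule is the more specific one. Harm requires a site to apply one sentence and overlook the footnote. This stands as evidence of intent and keeps the point minor. It does not repair 11.2.4, whose instruction to withdraw after 4 weeks is incompatible with on-study follow-up and carries no pointer to 11.3.3.

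Three stronger readings are tempting, and the documents do not support them.

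- *A reader might infer that 10.1 contradicts 10.2*, since 10.1 lists the same intolerance reason and then says "Subjects who discontinue treatment may remain in the study and continue protocol-required tests and assessments". That sentence is permissive and general. Mandatory withdrawal for one listed reason is compatible with it.
- *A reader might infer that subjects at high PML risk would be lost.* Section 5.3.2 ties most cases to counts below 0.5 x 10^9/L, and only part of the group below LLN would be that low. Under the early-stop assumption, subjects had at most 12 weeks of drug and are now off it. They cannot have met the protocol's withholding trigger of more than 24 weeks below 500/mm^3. The protocol also accepts care outside the study for subjects still below LLN at Week 96.
- *A reader might infer damage to the Week 48 analysis.* With about one subject or none involved, there is no material effect.

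**Conclusion.** Wrong as written, but minor. Section 11.2.4 and the intolerance bullet of 10.2 conflict with the lymphocyte follow-up set out in the other protocol sections and assumed in SAP 5.3.3. Version 2 lengthened that follow-up from 24 to up to 48 weeks and left the withdrawal sentence in 11.2.4 unchanged, which suggests an oversight rather than a choice.

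The textual conflict rests on no assumption, apart from the unseen Figure 3. The size does. About one affected subject or none depends on intolerance stops being few and early and on low counts accruing roughly evenly over the year. Later stops would raise the number towards the sensitivity figures. The descriptive recovery summary loses little. The reason to act is that sites should have one safety instruction.

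**What to change.** In 11.2.4, and in the intolerance bullet of 10.2 only, add:

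> unless the lymphocyte count is <LLN at discontinuation and the subject has not withdrawn consent, in which case the subject remains in the study for lymphocyte follow-up per Section 11.3.3 until the count is >=LLN, 48 weeks after the last dose, or study Week 96, whichever is first, and is then withdrawn.

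Two details matter. The end point should not be worded as the final Follow-Up Visit, because Table 1 sets that visit 4 weeks after the final dose and the cut-off could return. The clause should not attach to the lead-in of 10.2, where it would reach subjects who withdraw consent. Section 11.3.3 also keeps subjects still below LLN at 48 weeks on the Section 4 schedule. The clause stops at 48 weeks, as 7.2.3 does, and the sponsor should confirm that this is wanted.

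Cost: up to about 7 extra Lymphocyte Follow-Up Visits per affected subject (weeks 8, 12, 16, 20, 24, 36 and 48 after stopping), using the visit already in Table 2. If Table 1 visits are kept as well, those that do not coincide add 0 to 2 within the 48 weeks for a stop at Week 4, 8 or 12. At the upper early-stop figure this is 1.2 x 7 = 8.4 to 1.2 x 9 = 10.8 visits in the whole study, within the existing 104-week maximum. Off-drug samples from retained subjects could enter windows up to Week 48, but for about one subject or none.
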